6.2. Information to be Collected on Screening Failures

The informed consent date, demographics, and reason subject did not qualify for the study will be collected for all subjects determined to be screen failures. Adverse Events experienced by screen failure subjects will be collected from the date of signing consent to the day the subject is confirmed to be a screen failure. This information will be captured in the subject's source documents and appropriate CRF(s).

6.3. Entering a Subject Into the Study

Written consent must be obtained, all the screening evaluations must be completed, and eligibility criteria must be reviewed by the sponsor prior to contacting the IVRS to randomize a subject. Once redacted data is submitted to the sponsor, the sponsor (clinical research physician or designee) will review eligibility data and notify the Investigator that they agree with the eligibility criteria and site can proceed with the enrollment. Relevant information will also be recorded on the Screening Log.

Randomization will be stratified based on the following factors:

- a. Age (at time of induction therapy): 55-64 and ≥ 65
- b. Prior history of MDS or CMML: Yes / No
- c. Cytogenetic Risk category (at time of induction therapy): Intermediate risk / Poor risk
- d. Received consolidation therapy following induction: Yes / No

Randomization will occur by a central randomization procedure. Specific contact information and instructions will be provided individually to each study site.

Randomization of a subject in the IVRS can only be performed once the sponsor (clinical research physician or designee) has reviewed the subject's screening data and has reviewed the subject's entry into the study.

6.4. Baseline

Results obtained on Day 1 of Cycle 1 (just prior to the first dose of IP) from the physical examination, vital sign measurement, weight measurement and body surface area (BSA) calculation, and hematology or serum chemistry laboratory assessment will serve as the baseline values. If not available, the most recent screening results prior to Day 1 of Cycle 1 will be considered the baseline values.

FACIT-F, EQ-5D, and Physical Impairment Numeric Rating Scale should ideally be completed prior to dosing and prior to interaction with study personnel on Day 1 of Cycle 1.

6.5. Treatments

The first dose of IP should be administered within 3 days after randomization and within 4 months (± 7 days) of achieving CR/CRi status. The subject may not receive IP for each treatment cycle until all Day 1 procedures specified in [Table 1](#) have been completed, including physical examination, vital signs, weight, ECG, hematology, serum chemistry laboratory assessments and pregnancy test for FCBP.

IP dispensation

Investigational product should be dispensed on Day 1 of each cycle. Subjects should not receive any IP until all Day 1 assessments have been performed and the subject is confirmed to have met all criteria for continued treatment.

IP administration

Antiemetic medication (not supplied by the sponsor) should be administered 30 minutes prior to each IP dose. If there has been no nausea/vomiting, Investigator may choose to omit antiemetic

as required, provided this is clearly documented in the CRF. Investigational product is scheduled to be taken on Days 1 through 14 of each 28-day cycle. Refer to Section 8.2.3 for more information.

IP accountability

Investigational product accountability will be assessed by site personnel using pill counts and information provided by the subject or caregiver. Investigational product dosing information should be captured in the source documentation on Day 1 of each cycle beginning at Cycle 2 and at Treatment Discontinuation. Investigational product dosing information must also be entered on the appropriate CRF. Refer to Section 12 for more information.

Refer to [Appendix K](#) for Treatment Assignment, IP dispensation and IP accountability in the EP.

6.6. Safety

Safety assessments will consist of evaluating AEs and serious adverse events (SAEs) and concomitant medication/therapies used to treat them, secondary primary malignancy, hematology and serum chemistry parameters, body weight measurement, vital signs, physical examinations, and pregnancy testing (for FCBP subjects). Urinalysis and ECG will be repeated whenever clinically indicated during the double-blind treatment phase.

6.6.1. Adverse Events

All subjects will be monitored for AEs during the study. Assessments may include monitoring of the following parameters: the subject's clinical signs and symptoms, laboratory, pathological, radiological or surgical findings, physical examination findings, or results of any other appropriate test or procedure.

All AEs will be recorded by the Investigator from the time the subject signs the informed consent document (ICD) to 28 days after the last dose of IP or until the date of the last study visit, whichever is later. Adverse events and SAEs must be recorded on the AE CRF and in the subject's source documentation. All SAEs must be reported to Celgene Drug Safety within 24 hours of the Investigator's knowledge of the event by facsimile or other appropriate method, using the serious adverse event (SAE) Report Form, or approved equivalent form.

Information about common AEs of azacitidine can be found in the Investigator's Brochure (IB) or will be communicated between IB updates in the form of Investigator Notifications. This information about common side effects will also be included in the subject ICD and should be discussed with the subject as needed during the study.

6.6.2. Second Primary Malignancies

Second primary malignancies will be monitored as events of interest and should be included as part of the assessment of AEs throughout the duration of the study including post treatment follow-up period. Investigators are to report any second primary malignancy, regardless of causal relationship to IP, occurring at any time from signing of informed consent and until the last study visit, whichever period is longer as a SAE (considered to be at least "an important medical event" even if no other seriousness criteria apply). This information must also be documented on the appropriate pages of the CRF and in the subject's source documents. Documentation on the diagnosis of the second primary malignancy (eg, any confirmatory

histology or cytology or pathology results, X-rays, CT scans, etc.) must be provided at the time of reporting as an SAE. Subjects will be followed for SPMs as described in Section 6.14

6.6.3. Physical Examination

Physical examinations must be performed as indicated in Table 1.

6.6.4. Vital Signs Measurement

Vital signs (blood pressure, pulse and temperature) measurements must be performed as indicated in Table 1.

6.6.5. Weight

Weight measurements must be performed as indicated in Table 1. No dose adjustment should be made for weight loss or gain alone; however, the reason for weight loss (eg, significant nausea, vomiting, anorexia, etc.) or weight gain (e.g. peripheral edema) should be investigated to determine if a dose modification is warranted.

6.6.6. Hematology and Serum Chemistry Laboratory Evaluations

Hematology and serum chemistry laboratory analyses must be performed according to Table 1. The same parameters as required at screening should be evaluated. All samples should be sent to the central laboratory. In the event that an immediate laboratory assessment is required to acutely manage a subject, local laboratory tests may be used. In addition to collecting the local laboratory sample, a second sample should be collected and sent to the central laboratory.

Whenever a hematology sample is collected for a complete blood count, an unstained peripheral blood smear should be prepared and sent to the central laboratory. This unstained peripheral blood smear will be used to assess a manual blood count differential

When abnormal laboratory values or test results constitute an AE (ie, induce clinical signs/symptoms, require medical intervention, or result in IP dose reduction, interruption or discontinuation) they must be recorded on the AE CRF. Abnormal laboratory values or test results constitute AEs only if they induce clinical signs or symptoms, are considered clinically significant (eg, cause IP treatment modification or discontinuation), meet the criteria for a Serious Adverse Event, or require medical intervention. Any laboratory abnormality that meets one or more of these criteria should be recorded on the AE CRF using the appropriate term (ie, sign, symptom or diagnosis) associated with the event.

6.6.7. Pregnancy Testing (FCBP only)

A serum or urine pregnancy test (per Investigator's discretion) is to be done within 72 hours prior to starting study therapy in the double-blind treatment phase. The screening serum pregnancy test can be used as the test prior to starting study therapy in the double-blind treatment phase if it is performed within the 72-hour timeframe. A serum or urine pregnancy test (per Investigator's discretion) is to be done within 72 hours prior to IP administration on Day 1 of Cycle 2 and every treatment cycle thereafter, and at the Treatment Discontinuation visit. The subject may not receive IP until the Investigator has verified that the result of the pregnancy test is negative. Pregnancy testing at screening is provided in Section 6.1.

6.6.8. Concomitant medications/significant non-drug therapies/concomitant procedures

All concomitant over-the-counter medications including vitamins/minerals and herbal supplements taken for general health and well-being and prescription medications including anti-infectives for prophylaxis and/or treatment of an infection that are taken from Cycle 1, Day 1 up to 28 days after the last dose of IP or up to the Treatment Discontinuation visit, whichever period is longer, must be recorded on the appropriate page(s) of the CRF.

6.7. Efficacy

IWG Response

International Working Group response assessment will be assessed at Cycles 3, 6, 9, 12, 15, 18, 21, 24, 30, 36, and the Treatment Discontinuation visit. After Cycle 36, IWG response assessment will be performed if clinically indicated at the discretion of the Investigator. Subjects should be assessed for CR/CRi status maintenance or disease relapse.

Bone Marrow Aspirate, Biopsy and Peripheral Blood Smear

Bone marrow aspirate (or biopsy if adequate aspirate is not attainable) samples during the double-blind treatment phase should be collected on Day 1 (\pm 7 days) of Cycles 3, 6, 9, 12, 15, 18, 21, 24, 30, 36, and the Treatment Discontinuation visit. After Cycle 36, bone marrow aspiration collection and evaluation will occur if clinically indicated at the discretion of the Investigator.

Additional bone marrow samples should be collected as clinically indicated. A bone marrow biopsy must be collected if adequate aspirate is not attainable. Whenever a bone marrow sample is collected, a peripheral blood smear is to be prepared.

Instructions for submission of bone marrow samples are provided in Study Reference and/or Study Central Laboratory Manual.

Cytogenetics

Bone marrow cytogenetic testing is to be completed whenever a bone marrow aspirate (or biopsy if adequate aspirate is not attainable - note that specific handling of the biopsy is required if to be used for cytogenetics testing [see the Study Reference and/or study's Central Laboratory Manual for handling instructions]) is obtained for efficacy assessment.

Follow-Up AML Therapies

All discontinued subjects, regardless of reason for discontinuation, should be followed for subsequent AML therapies every month for the first year and every three months thereafter until death, loss to follow-up, withdrawal of consent from further follow-up, or study closure. Subsequent AML therapy follow-up can be performed via the telephone.

Survival Follow-Up

All discontinued subjects, regardless of reason for discontinuation, should be followed for survival every month for the first year and every three months thereafter until death, lost to follow-up, withdrawal of consent from further follow-up, or study closure. The survival follow-up can be performed via telephone.

[REDACTED]

[REDACTED]

- [REDACTED]
- [REDACTED]
- [REDACTED]

[REDACTED]

[REDACTED]

[REDACTED]

[REDACTED]

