25. FACIT–Fatigue Scale ([Appendix F](#)), EQ-5D ([Appendix G](#)), and exploratory quality-of-life (QoL) (Physical Impairment Numeric Rating Scale, [Appendix H](#)) questionnaires, should ideally be completed prior to dosing and when feasible, prior to interaction with study personnel on Day 1 of every cycle, beginning on Day 1 of Cycle 1, and at study discontinuation.
26. Bone marrow samples for biomarker assessment are desired but optional and subject must consent to the collection of these samples. Samples should be collected when bone marrow is collected at protocol specified time points and when bone marrow is collected to confirm a response (CR or CRi) or relapse. Biomarker analysis will only be performed using these samples when sufficient bone marrow sample material remains (optimally 10-15 mL). Sample collection, processing, storage, and shipment procedures will be provided in the Study Reference and/or Study Central Laboratory Manual.
27. Mandatory sample collection for PK. Subjects should consent to the collection of these samples by signing the ICD, mandatory sample collection section. Two blood samples (3 mL/sample) for azacitidine PK assessment will be collected at least 2 hours apart on Day 1 of Cycles 1, 3, and 6 between 0.5 and 6.0 hours post IP administration (Section [6.11](#)). Blood samples must be processed and plasma harvested and stored according to the instructions in the Study Reference and/or Study Central Laboratory Manual.
28. The study visit window in the double-blind treatment phase is ± 3 days for Cycles 1, 2, 3 and beyond, unless noted otherwise for a particular assessment. Study visits should also take into account the subject's IP supply. Only 1 cycle of IP will be dispensed to the subject on Day 1 of each cycle. Day 1 of Cycles 2 and beyond may be delayed from Day 28 of the prior cycle in order for subjects to recover from toxicity and meet criteria for re-treatment (Section [8.2.6](#)). During follow-up, the study visit window is ± 7 days for visits scheduled monthly (including the follow-up visit 28 days after last dose if necessary) or ± 14 days for visits scheduled every 3 months. One cycle (one month) is considered as 28 days (ie, 4 weeks).

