8.2.7. Re-treatment Criteria

Prior to the start of each cycle, subjects will have laboratory assessments performed to evaluate organ function. In order to proceed to the next cycle, subjects must continue to meet entry criteria regarding renal and hepatic function (see Section 7.2). Thus, subjects will have laboratory assessments performed to evaluate organ function prior to starting each cycle (including Cycle 1). Because of the time it takes to obtain results from the central laboratory, samples should be collected early enough prior to starting the next cycle in order to allow sufficient time for review. In the event that immediate laboratory assessment is needed, local laboratory measurement is acceptable for starting the next cycle pending the outcome of the central laboratory assessment (ie, in addition to collecting the local laboratory sample, a second sample should be collected and sent to the central laboratory).

The start of the next cycle will be delayed if the subject does not meet entry criteria regarding renal and hepatic function. If there is a delay of more than 42 days (6 weeks) in the start of the next cycle, the Medical Monitor must be consulted. Study treatment should be discontinued if there is a delay of more than 56 days (8 weeks) in the start of the next cycle, unless, in the opinion of the investigator and the Medical Monitor, the subject is experiencing clinical benefit. Justification of the subject continuing in the study must be recorded in the source documents.

Prior to discontinuing a subject for reasons other than those listed in Section 8.2.5, the investigator should contact the Medical Monitor and forward appropriate supporting documents for review and discussion.

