10.3. Sample Size and Power Considerations

The equality of OS curves will be compared between the azacitidine and placebo treatment groups using a stratified log-rank test. Assuming a median OS of 16 months in the placebo treated group (), a median OS of 22.9 months in the azacitidine treated group (43% improvement), and a study duration of 60 months with a drop-out rate of 5% from both treatment groups, over the duration of the study, this design requires 330 deaths and approximately 460 subjects (230 per treatment arm) to be randomized in order to achieve at least

90% power to detect a constant hazard ratio of 0.70 and demonstrate a statistically significant difference in OS. It is assumed that the OS distribution is exponential with a constant failure (hazard) rate and that accrual is non-uniform during an accrual period of 36 months with 25% of the subjects accrued during each of the first 2 years of enrollment (50% accrued at 24 months) and the remaining 50% accrued during the last year of enrollment. Sample size calculations are based on a one-sided alpha of 0.025 with one interim analysis for futility after 30% of the events have occurred.

Sample size was calculated using the East[®] Version 5.4 software system ([REDACTED]).

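### Relapse checks follow cycle numbers that can slip for toxicity, so an arm with more delays has its relapses dated later and the RFS comparison is modestly biased towards it

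*Protocol*

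**What the plan says.** **Assessment clock.** Protocol Section 6.7 states: "International Working Group response assessment will be assessed at Cycles 3, 6, 9, 12, 15, 18, 21, 24, 30, 36, and the Treatment Discontinuation visit". Table 1 footnotes 17 and 21 give the same cycles, with marrows due on Day 1 (±7 days). Blood counts with a central smear are also placed on cycle days: Days 1, 8, 15 and 22 of Cycles 1 and 2, then Days 1 and 15, with Day 15 optional from Cycle 25.

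**Cycle starts can move.** Under Table 1 footnote 28, Day 1 of Cycle 2 and later "may be delayed from Day 28 of the prior cycle in order for subjects to recover from toxicity". Section 8.2.7 sets the outer limit: "Study treatment should be discontinued if there is a delay of more than 56 days (8 weeks) in the start of the next cycle", with an exception for clinical benefit. Nothing keeps a marrow on its planned calendar date when its cycle slips.

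**Analysis.** SAP Section 11.3.1 dates relapse when marrow or blood first documents it. An event more than 200 days after the previous marrow is censored (SAP Table 2). RFS is tested after OS in a fixed sequence, with a confirmatory stratified log-rank p-value (SAP Sections 11.1 and 11.3.1). The RFS sensitivity analyses are mITT, investigator-assessed relapse and EMA censoring rules.

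**The concern.** Each delayed cycle start pushes back every later scheduled marrow and smear for that subject. If delays are more common in one arm, two subjects whose disease returns on the same day are dated differently, and the later date falls in the arm with more delays. A log-rank test reads that as longer relapse-free survival.

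RFS is the only endpoint besides OS with a formal test. None of its planned sensitivity analyses deals with when subjects were examined: the EMA version drops the 200-day rule but still dates relapse at detection. The 200-day cut-off was itself derived without allowing for toxicity delays, so a delay can remove an event as well as postpone it.

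**Working it through.** **1. The plan's own figures.** The OS calculation says "this design requires 330 deaths and approximately 460 subjects (230 per treatment arm) to be randomized", for "90% power to detect a constant hazard ratio of 0.70 and demonstrate a statistically significant difference in OS". Schoenfeld's formula gives 4 × (1.960 + 1.282)² / (ln 0.70)² = 42.03 / 0.1272 = 330.4, so 331 after rounding up. Power with 330 deaths is 0.8997. The figure is reproduced. No RFS median, event count or power is stated.

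SAP Table 2 derives 31 × 3 + 7 = 100 days for consecutive marrows, which allows only ±3 days per cycle. For the six-cycle gaps (Cycles 24 to 30 and 30 to 36) the same arithmetic gives 31 × 6 + 7 = 193 days, just under 200.

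**2. Calendar drift.** The documents give no delay rates. Assume a 14-day delay with probability p per cycle in one arm only:

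| p | Mean cycle (28 + 14p) | Mean shift at Cycle 12 Day 1 (11 starts) | Mean shift at Cycle 24 Day 1 (23 starts) |
|---|---|---|---|
| 0.1 | 29.4 days | 11 × 1.4 = 15.4 days | 23 × 1.4 = 32.2 days |
| 0.3 | 32.2 days | 11 × 4.2 = 46.2 days | 23 × 4.2 = 96.6 days |

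**3. The 200-day rule.** Six 28-day cycles take 168 days, leaving 32 days, or 32 / 6 = 5.3 days per cycle. One 56-day delay gives 168 + 56 = 224 days. Three 14-day delays give 168 + 42 = 210. The chance of three or more in six starts is 1 − (0.9⁶ + 6 × 0.1 × 0.9⁵ + 15 × 0.1² × 0.9⁴) = 0.016 at p = 0.1, and 0.256 by the same formula at p = 0.3.

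**4. RFS under no true difference.** The simulations used 230 per arm, identical relapse onset (exponential, median 6 or 10 months, assumed), 14-day delays in 10-30% of one arm's cycles and an unstratified log-rank test. Marrow windows were ±3 days without deaths, or ±7 days with non-relapse deaths (median 60 months, assumed).

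| Relapse found by | Setting | RFS HR | One-sided rejection (nominal 2.5%) |
|---|---|---|---|
| Scheduled marrow only | ±3 days, no deaths | 0.927-0.971 | 4.4-10.5% |
| Scheduled marrow only | ±7 days, deaths (two runs) | 0.945-0.973; 0.94-0.97 | 3.7-8.2%; 5.0-9.5% |
| Half by blood | ±3 days, no deaths | 0.966-0.981 | 4.2-5.4% |
| Half by blood | ±7 days, deaths (two runs) | 0.980-0.988; about 0.975-0.99 | 2.6-3.7%; 3.1-4.9% |
| 80% by blood | ±7 days, deaths | 0.988-0.993 | 2.5-3.1% |

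Without delays, rejection was 1.8-3.8%. Monte Carlo error is about 0.4 to 1 percentage point. The bias does not rise steadily with the delay rate. Detections cluster at visits, and a small consistent shift already places one arm's cluster after the other's.

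**5. Heavier delays.** These runs assumed 25% of cycles delayed by a mean of 12 days, or 50% by a mean of 14 days, with medians of 6, 10 or 16 months and the 200-day rule applied.
- Marrow only: HR 0.90-0.95, rejection 6.9-17.0%.
- Half by blood: HR 0.92-0.98, rejection 4.5-12.0%.
- 80% by blood (50% delayed): HR 0.93-0.99, rejection 3.0-10.1%.
- Effect of the 200-day rule at a 16-month median, 50% delayed, marrow only: HR 0.900 with it and 0.952 without it.
- No delays: HR 0.997-1.001, rejection 2.1-2.6%.

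**The case against.** The strongest reply is that scheduled marrows are not the only route to a relapse date. SAP Section 11.3.1 also accepts any blood blasts confirmed by marrow within 100 days, or two blood readings of at least 5% within 30 days. Protocol Section 6.7 asks for extra marrows when clinically indicated, and Table 1 footnote 17 allows aspirates for toxicity assessment, which would bring detection forward in the more toxic arm. Adding a marrow in 25-50% of delayed cycles moved the marrow-only HR at 30% delays from 0.957-0.973 to 0.976-0.992. This stands: it shrinks the effect, and with most relapses found by blood the excess cannot be told from simulation error at 10-30% delays. It does not remove the mechanism, because scheduled smears follow cycle days too.

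The delay rates are also assumptions. Section 8.2.7 conditions the next cycle on renal and hepatic criteria only, and most rules in Protocol Table 2 interrupt dosing rather than delay a cycle. This stands as well.

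SAP Section 9.1 already summarizes average cycle length by arm. That would reveal an imbalance, but it is an exposure summary. It neither shows marrow intervals nor adjusts RFS.

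**Conclusion.** The mechanism follows from the documents and no planned analysis addresses it. The bias is modest. With 14-day delays in 10-30% of one arm's cycles and relapse medians of 6 to 10 months, the null RFS HR is about 0.94-0.97 (rejection about 4-10%) if only scheduled marrows find relapse, and about 0.97-0.99 (about 3-5%) if half are found by blood. It is close to nominal if most are found by blood or unscheduled marrows. Heavier delays or longer medians, together with the 200-day rule, would enlarge it.

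A reader might infer three stronger things that the documents do not support:
- **That azacitidine's RFS will look better without any effect.** More delays on active drug are plausible, but no delay rates by arm are given, so the direction is conditional.
- **That the RFS false-positive rate is 10% or more.** Rates near 10% at the 10-30% delays need relapse to be found only at scheduled marrows, and higher rates also need heavier assumed delays.
- **That the trial's overall error control fails.** OS dating does not depend on cycles. If the drug affects neither endpoint, a formal RFS claim first needs a false OS win, so it cannot exceed 2.5% one-sided. The inflation matters where OS benefit is real and RFS benefit is not.

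**What to change.** **Protocol Section 6.7 and Table 1 footnotes 17 and 21.** For any marrows still to be collected, tie the marrow/IWG visit to weeks from randomization at the same planned spacing, ±7 days, whatever the dosing delay. With 28-day cycles, Day 1 of Cycles 3 to 24 corresponds to week 8 and then every 12 weeks to week 92. Cycles 30 and 36 correspond to weeks 116 and 140.

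**SAP Section 11.3.1.** Add a stratified, interval-censored ITT sensitivity analysis of RFS, with relapse placed between the last marrow without relapse and the first marrow or blood evidence. It uses dates already recorded and is the main remedy for marrows already taken.

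**Reporting.** Tabulate actual days between marrows by arm, beside the cycle-length summary in SAP Section 9.1. Balanced intervals would largely settle the question. Unbalanced ones should be shown with the interval-censored result next to the confirmatory p-value.

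**Cost.** Some marrow visits will not fall on a cycle Day 1, and one supportive analysis and one table are added. The number of marrows stays about the same and no dosing rule changes.
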